Treatment comparisons for continuous efficacy and health outcomes variables may also be made using analysis of covariance (ANCOVA) for primary and key secondary objectives. When an ANCOVA model is used, the model includes region, baseline disease severity, treatment group, and baseline value. Treatment LSM will be estimated within the framework of the ANCOVA using type 3 sums of squares. Reported differences in LSM and associated p-values, standard errors and 95% CI will be used for statistical inference. Treatment-by-region interaction will also be added to the model for sensitivity purposes and is discussed in Section 6.5.

Beginning on Day 14 a Cox proportional hazard (CPH) model of time (in days) to first observance of a 4-point itch reduction with effects for treatment, region, baseline mean itch, and disease severity will be used to test for treatment differences from placebo. For this analysis, daily itch scores will be compared to the baseline to determine if a 4-point itch reduction has been achieved in patients with a baseline itch of at least 4. The baseline for itch NRS is defined in Section 6.2.2. The day on which the first 4-point reduction in itch NRS is achieved will be modeled. If any significant treatment difference is observed then the same analysis will be performed on Day 13. This process of evaluating at the next lowest day will proceed until no significant differences are observed. No adjustments for multiple tests and multiple comparisons will be used. This analysis uses the Primary Censoring Rule for patients who are rescued or permanently discontinue study drug (see Section 6.4). Missing daily itch data will be replaced using NRI rule which means missing data is replaced with a non-response which would entail replacing missing values with a time to event of > 14 days, censored; >13 days, censored, etc., depending on the window being used. If the model assumptions for the CPH model do not hold, a log-rank test will be used.

Restricted mean survival time will be evaluated at Days 2, 3, 4 and 5 as an exploratory analysis. The model will include terms for baseline disease severity (IGA), baseline itch, region, and treatment group.

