6.4. Handling of Dropouts or Missing Data

Intercurrent events (ICH E9 R1) are events which occur after the treatment initiation and make it impossible to measure a variable or influence how it would be interpreted.

Depending on the estimand being addressed, different methods will be used to handle missing data as a result of intercurrent events. Intercurrent events can occur through the following:

- application of one of the censoring rules (including after permanent study drug discontinuation or after rescue therapy)
- discontinuation
- missing an intermediate visit prior to discontinuation or rescue
- lost to follow-up.

Non-censor intercurrent events are events that are not due to the application of any censoring rule, i.e., the last 3 items in the list above.

Note that as efficacy and health outcome data can accrue after a patient permanently discontinues study drug or begins rescue therapy, specific general censoring rules to the data will be applied to all efficacy and health outcome observations subsequent to these events depending on the estimand being addressed. These specific censoring rules are described below.

The *primary censoring rule* will censor efficacy and health outcome data after permanent study drug discontinuation or after rescue therapy. This censoring rule will be applied to all continuous and categorical efficacy and health outcome endpoints. This censoring rule is equivalent to using all the data up to rescue.

A *secondary censoring rule* will only censor efficacy and health outcome data after permanent study drug discontinuation. This sensitivity analysis will include all observed values up to study drug discontinuation. The secondary censoring rule will be applied to primary and key secondary efficacy and health outcome endpoints as sensitivity analyses.

Table JAHL.6.1 describes the planned imputation methods for efficacy and health outcome endpoints with associated censoring rules. Sections 6.4.1 through 6.4.5 summarize the methodology of each imputation rule.

Table JAHL.6.1. Imputation Techniques for Various Variables

Efficacy and Health Outcome Endpoints	Imputation Method
IGA(0,1), EASI75, 4-point Itch NRS improvement, EASI90, SCORAD75	NRI ^{ab} , pMI ^a , Tipping point ^a
EASI percent change, ADSS Item 2 change, Skin Pain NRS change	MMRM ^{ab} , mLOCF ^a , pMI ^a
All remaining categorical measures	NRI ^a
All remaining continuous efficacy and health outcome measures	MMRM ^a , mLOCF ^a

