6.6. Multiple Comparisons/Multiplicity

The primary and key secondary endpoints will be adjusted for multiplicity in order to control the overall family-wise Type I error rate at a 2-sided alpha level of 0.05.

The following is a list of primary and key secondary endpoints to be tested. The subscript for **H** denotes dose (4-mg, 2-mg, 1-mg), the numerical identifier of the endpoint within the dose, and the type of hypothesis (0 for null, 1 for alternative), respectively.

Primary Null Hypotheses:

- **H_{4,1,0}:** Proportion of baricitinib 4-mg patients achieving IGA of 0 or 1 with a ≥ 2 -point improvement from baseline at Week 16 is less than or equal to the proportion of placebo patients achieving IGA of 0 or 1 with a ≥ 2 -point improvement from baseline at Week 16 [IGA0-1]
- **H_{2,1,0}:** Proportion of baricitinib 2-mg patients achieving IGA of 0 or 1 with a ≥ 2 -point improvement from baseline at Week 16 is less than or equal to the proportion of placebo patients achieving IGA of 0 or 1 with a ≥ 2 -point improvement from baseline at Week 16 [IGA0-1]

Key Secondary Null Hypotheses:

- **H_{4,2,0}:** Proportion of baricitinib 4-mg patients achieving EASI75 is less than or equal to the proportion of placebo patients achieving EASI75 at Week 16 [EASI75]
- **H_{4,3,0}:** Proportion of baricitinib 4-mg patients achieving a 4-point improvement in Itch NRS is less than or equal to the proportion of placebo patients achieving a 4-point improvement in Itch NRS at Week 16 [ITCH W16]
- **H_{4,4,0}:** Percent change from baseline in EASI score for baricitinib 4-mg patients is greater than or equal to the percent change from baseline in EASI score for placebo patients at Week 16 [EASI PCFB]
- **H_{4,5,0}:** Proportion of baricitinib 4-mg patients achieving a 4-point improvement in Itch NRS is less than or equal to the proportion of placebo patients achieving a 4-point improvement in Itch NRS at Week 4 [ITCH W4]
- **H_{4,6,0}:** Proportion of baricitinib 4-mg patients achieving SCORAD75 is less than or equal to the proportion of placebo patients achieving SCORAD75 at Week 16 [SCORAD75]
- **H_{4,7,0}:** Proportion of baricitinib 4-mg patients achieving EASI90 is less than or equal to the proportion of placebo patients achieving EASI90 at Week 16 [EASI 90]
- **H_{4,8,0}:** Mean change from baseline in Skin Pain NRS for baricitinib 4-mg patients is greater than or equal to the mean change from baseline in Skin Pain NRS for placebo patients at Week 16 [PAIN W16]

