6.11. Efficacy Analyses

The general methods used to summarize efficacy data, including the definition of baseline value for assessments are described in Section 6.2. The censoring rules applied to data as well as imputation methods are described in Section 6.4.

[Table JAHL.6.4](#) provides the descriptions and derivations of the primary, secondary, and exploratory efficacy outcomes.

[Table JAHL.6.5](#) provides the detailed analyses including analysis type, method and imputation, population, time point, and comparisons for efficacy analyses.

Table JAHL.6.4. Description and Derivation of Primary, Secondary and Exploratory Efficacy Outcomes

Measure	Description	Variable	Derivation / Comment	Imputation Approach if Missing Components
Validated Investigator's Global Assessment for AD (IGA)	The validated Investigator's global assessment of the patient's overall severity of their AD, based on a static, numeric 5-point scale from 0 (clear) to 4 (severe). The score is based on an overall assessment of the degree of erythema, papulation/induration, oozing/crusting, and lichenification.	IGA score	Single item. Range: 0 to 4 0 represents "clear" 4 represents "severe"	Single item, missing if missing.
		Change from baseline in IGA score	Change from baseline: observed IGA score – baseline IGA score	Missing if baseline or observed value is missing.
		
 ▪ IGA [0,1] with ≥ 2-point improvement ▪ IGA [0] 	
 ▪ Observed score of 0 or 1 and change from baseline ≤ -2 ▪ Observed score of 0 	
 ▪ Missing if baseline or observed value is missing. ▪ Single item, missing if missing.

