Eczema Area and Severity Index (EASI)	The EASI assesses objective physician estimates of 2 dimensions of atopic dermatitis – disease extent and clinical signs (Hanifin et al 2001) – by scoring the extent of disease (percentage of skin affected: 0 = 0%; 1 = 1-9%; 2 = 10-29%; 3 = 30-49%; 4 = 50-69%; 5 = 70-89%; 6 = 90-100%) and the severity of 4 clinical signs (erythema, edema/papulation, excoriation, and lichenification) each on a scale of 0 to 3 (0 = none, absent; 1 = mild; 2 = moderate; 3 = severe) at 4 body sites (head and neck, trunk, upper limbs, and lower limbs). Half scores are allowed between severities 1, 2 and 3. Each body site will have a score that ranges from 0 to 72, and the final EASI score will be obtained by weight-averaging these 4 scores. Hence, the final EASI score will range from 0 to 72 for each time point.	EASI score	Derive EASI region score for each of head and neck, trunk, upper limbs, and lower limbs as follows: $\text{EASI}_{\text{region}} = (\text{Erythema} + \text{edema/papulation} + \text{Excoriation} + \text{Lichenification}) * (\text{value from percentage involvement})$, where erythema, edema/papulation, excoriation, and lichenification are evaluated on a scale of 0 to 3 and value from percentage involvement is on a scale of 0 to 6. Then total EASI score is as follows: $\text{EASI} = 0.1 * \text{EASI}_{\text{head and neck}} + 0.3 * \text{EASI}_{\text{trunk}} + 0.2 * \text{EASI}_{\text{upper limbs}} + 0.4 * \text{EASI}_{\text{lower limbs}}$	N/A – partial assessments cannot be saved.
		
 ▪ Change from baseline in EASI score ▪ Percent change from baseline EASI score 	Change from baseline: observed EASI score – baseline EASI score % change from baseline: $100 \times \frac{\text{Observed score} - \text{Baseline}}{\text{Baseline}}$	Missing if baseline or observed value is missing.
		EASI50	% Improvement in EASI score from baseline $\geq 50\%:$	Missing if baseline or observed value is missing.

			% change from baseline ≤ -50	
		EASI75	% Improvement in EASI score from baseline $\geq 75\%$: % change from baseline ≤ -75	Missing if baseline or observed value is missing.
		EASI90	% Improvement in EASI score from baseline $\geq 90\%$: % change from baseline ≤ -90	Missing if baseline or observed value is missing.

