6.12. Health Outcomes/Quality-of-Life Analyses

The general methods used to summarize health outcomes and quality-of-life measures, including the definition of baseline value for assessments are described in Section 6.1.

Health outcomes and quality-of-life measures will generally be analyzed according to the formats discussed in Section 6.11.

[Table JAHL.6.6](#) includes the descriptions and derivations of the health outcomes and quality-of-life measures.

[Table JAHL.6.7](#) provides the detailed analyses including analysis type, method and imputation, population, time point, and comparisons for health outcomes and quality-of-life measures.

Additional psychometric analyses will be performed by Global Patient Outcomes Real World Evidence at Lilly and documented in a separate analysis plan.

Table JAHL.6.6. Description and Derivation of Health Outcomes and Quality-of-Life Measures

Measure	Description	Variable	Derivation / Comment	Imputation Approach if Missing Components
Itch Numeric Rating Scale (NRS)	The Itch Numeric Rating Scale (NRS) is a patient-administered, 11-point horizontal scale anchored at 0 and 10, with 0 representing “no itch” and 10 representing “worst itch imaginable.” Overall severity of a patient’s itching is indicated by selecting the number that best describes the worst level of itching in the past 24 hours (Naegeli et al. 2015; Kimball et al. 2016). Refer to Section 6.2.2 for details on how to calculate the weekly score which will be used in the continuous analysis.	Itch NRS score	Single item; range 0-10. Refer to Section 6.2.2 on how to derive the visit score.	Refer to Section 6.2.2 on how to derive the weekly visit score.
		▪ Change from baseline in Itch NRS ▪ Percent change from baseline in Itch NRS	Change from baseline: observed Itch score – baseline Itch score % change from baseline: $100 \times \frac{\text{Observed score} - \text{Baseline}}{\text{Baseline}}$	Missing if baseline or observed value is missing.
		4-point Itch improvement in subgroup of patients with baseline Itch NRS ≥ 4	Change from baseline ≤ 4 and baseline ≥ 4	Missing if baseline is missing or < 4 or observed value is missing.

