Itch Numeric Rating Scale (NRS)	
 • Itch NRS score • Change from baseline in Itch NRS score 	MMRM	ITT	Bari 4-mg or Bari 2-mg or Bari 1-mg vs PBO; Week 4, 16	Secondary Analysis
		ANCOVA using mLOCF	ITT	Bari 4-mg or Bari 2-mg or Bari 1-mg vs PBO; Week 4, 16	Sensitivity Analysis
		pMI	ITT	Bari 4-mg or Bari 2-mg or Bari 1-mg vs PBO; Week 4, 16	Sensitivity Analysis
	Percent change from baseline Itch score	MMRM	ITT	Bari 4-mg or Bari 2-mg or Bari 1-mg vs PBO; Week 1, 16	Secondary Analysis
		ANCOVA using mLOCF	ITT	Bari 4-mg or Bari 2-mg or Bari 1-mg vs PBO; Week 1, 16	Sensitivity Analysis
	Proportion of patients achieving a 4-point improvement in Itch NRS in subgroup of patients who had baseline Itch NRS ≥ 4	Logistic regression using NRI	ITT	Bari 4-mg or Bari 2-mg or Bari 1-mg vs PBO; Week 1, 2, 4, 16	Key Secondary Analysis
			PPS	Bari 4-mg or Bari 2-mg or Bari 1-mg vs PBO; Week 16	Sensitivity analysis
		Logistic regression using pMI and Tipping Point	ITT	Bari 4-mg or Bari 2-mg or Bari 1-mg vs PBO; Week 16	Sensitivity analysis
	Number of Itch-free (Itch NRS = 0) Days	Descriptive statistics	ITT	No comparisons; Week 12 to 16	Exploratory Analysis
Skin Pain Numeric Rating Scale (NRS)	
 • Skin Pain NRS score • Change from baseline in Skin Pain NRS score 	MMRM	ITT	Bari 4-mg or Bari 2-mg or Bari 1-mg vs PBO; Week 16	Key Secondary Analysis
			PPS	Bari 4-mg or Bari 2-mg or Bari 1-mg vs PBO; Week 16	Sensitivity analysis
		ANCOVA using mLOCF	ITT	Bari 4-mg or Bari 2-mg or Bari 1-mg vs PBO; Week 16	Sensitivity Analysis
		pMI	ITT	Bari 4-mg or Bari 2-mg or Bari 1-mg vs PBO; Week 16	Sensitivity analysis
	Number of Skin Pain-free (Skin pain NRS = 0) Days	Descriptive statistics	ITT	No comparisons; Week 12 to 16	Exploratory Analysis

Measure	Variable	Analysis Method (Section 6.2.3)	Population (Section 6.2.1)	Comparison/Time Point	Analysis Type
Atopic Dermatitis Sleep Scale (ADSS)	
 • ADSS item scores • Change from baseline in ADSS item scores 	MMRM	ITT	Bari 4-mg or Bari 2-mg or Bari 1-mg vs PBO; Week 1, 16	Key Secondary Analysis
			PPS	Bari 4-mg or Bari 2-mg or Bari 1-mg vs PBO; Week 16	Sensitivity analysis
		ANCOVA using mLOCF	ITT	Bari 4-mg or Bari 2-mg or Bari 1-mg vs PBO; Week 1, 16	Sensitivity Analysis
		pMI	ITT	Bari 4-mg or Bari 2-mg or Bari 1-mg vs PBO; Week 16	Sensitivity analysis

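### The SAP's itch responder rule has lost its minus sign: a change of 4 or less counts as response, where a 4-point improvement requires -4 or less

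*SAP*

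**What the plan says.** SAP Section 6.12, Table JAHL.6.6, has a row for 4-point itch improvement among patients with baseline Itch NRS of at least 4. Its derivation is "Change from baseline ≤ 4 and baseline ≥ 4". The row above gives the sign convention: "Change from baseline: observed Itch score – baseline Itch score". The scale runs from 0 (no itch) to 10 (worst imaginable). Section 6.2.4 gives the same convention for change from baseline in general.

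The other responder rules carry the minus sign. In Table JAHL.6.4 the IGA rule is "Observed score of 0 or 1 and change from baseline ≤ -2", and the EASI75 and SCORAD75 rules both use "change from baseline ≤ -75".

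Everywhere else the itch endpoint is described as a fall in score:

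- Table JAHL.6.7 lists the key secondary analysis as "Proportion of patients achieving a 4-point improvement in Itch NRS in subgroup of patients who had baseline Itch NRS ≥ 4".
- Section 6.6 states the 4-mg null hypotheses as "Proportion of baricitinib 4-mg patients achieving a 4-point improvement in Itch NRS is less than or equal to" the placebo proportion, and words the other doses the same way.
- Section 6.2.3 compares daily scores with baseline to "determine if a 4-point itch reduction has been achieved".

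Neither document states a signed numeric threshold for itch response anywhere else.

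**The concern.** The derivation contradicts its own label. Under the table's convention improvement is negative, so a threshold of +4 accepts any patient who has not worsened by more than 4 points.

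The output might not reveal the error. The primary censoring rule "will censor efficacy and health outcome data after permanent study drug discontinuation or after rescue therapy", and nonresponder imputation (NRI) then makes those patients, and any with missing scores, nonresponders. Nearly all remaining patients would pass. The arm's response rate would be close to one minus its censored or missing share, which could look like a believable itch result while mainly reflecting retention without rescue. A test could reject, or fail to reject, for reasons unrelated to itch. Because Section 6.6 passes alpha on as hypotheses are rejected, a wrong itch result could also affect other tests.

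The rule also feeds the per-protocol, placebo multiple imputation (pMI), tipping-point and subgroup analyses of the Week 16 itch response. Under pMI the binary outcome is derived from imputed scores, so almost every imputed patient would become a responder. pMI and NRI would then differ by about the censored share.

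**Working it through.** The plan gives no figure that depends on this rule, so there is nothing to reproduce. The check has four steps.

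**1. Reach.** Section 6.6 lists 12 hypotheses per dose: 12 × 3 doses = 36. Itch response appears at Weeks 1, 2, 4 and 16: 4 × 3 = 12 of the 36.

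**2. The two rules on whole-number scores.** Let b be baseline (4 to 10) and o the observed score (0 to 10), giving 7 × 11 = 77 pairs, with change = o − b.

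- As written, response needs o ≤ b + 4. The only failures are (b, o) = (4, 9), (4, 10) and (5, 10), so 77 − 3 = 74 pairs respond. These include all 7 no-change pairs and 18 of the 21 worsening pairs. For b ≥ 6, b + 4 is at least 10, so failure is impossible.
- As intended, response needs o ≤ b − 4. The count is 1 + 2 + … + 7 = 28, with no unchanged or worsened pair among them.

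Weekly itch scores are means and need not be whole numbers; the grid is only an illustration.

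**3. Response rates in uncensored patients.** The documents give no itch distribution, so these inputs are assumed: baseline mean 6, 6.7 or 7.5; SD 1.2, 1.6 or 2.0, truncated to 4–10; mean fall 0, 1, 2 or 3; SD of change 2.0, 2.5 or 3.0; observed scores clipped to 0–10. That makes 3 × 3 × 4 × 3 = 108 scenarios, each simulated with 400,000 patients.

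| Rule | Responders across scenarios |
|---|---|
| As written (≤ 4) | about 96% to >99.9% |
| As intended (≤ -4) | about 2.2% to 37.1% |

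**4. What the test would then compare.** Taking 99% response among uncensored patients, the arm rate after NRI is 0.99 × (1 − c), where c is the censored or missing share:

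- c = 0%: 99%
- c = 20%: 0.99 × 0.80 = 79%
- c = 30%: 0.99 × 0.70 = 69%
- c = 50%: 0.99 × 0.50 = 50%

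Suppose itch does not differ between arms and only c does. The rejection probabilities below come from exact binomial enumeration of an unadjusted two-proportion z test at two-sided 0.025. This simplifies the SAP's Firth logistic model. The first set uses 240 placebo and 120 active patients; the second assumes 85% have baseline ≥ 4 (204 and 102).

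| Censored: placebo vs active | 240 vs 120 | 204 vs 102 | Favours |
|---|---|---|---|
| Equal (20%, 30% or 50% in both) | about 1% | about 1% | baricitinib |
| 20% vs 15% | 12% | 10% | baricitinib |
| 20% vs 10% | 55% | 47% | baricitinib |
| 30% vs 20% | 40% | 34% | baricitinib |
| 40% vs 20% | 95% | 91% | baricitinib |
| 10% vs 20% | 61% | 54% | placebo |

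About 1% is the nominal rate in one direction (0.025 / 2 = 1.25%).

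**The case against.** The strongest reply is that the intent is beyond doubt. The row label, objectives, hypotheses, analysis table and subgroup section all say improvement, and the Cox model text says reduction. Harm requires a programmer to follow the cell against all of these. That is fair, and a careful programmer would probably notice. But a derivation table is what gets programmed, and no other section supplies the signed threshold.

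A minus sign could also have been lost when the table was read from PDF. This cannot be wholly excluded. It survived in the parallel IGA, EASI and SCORAD rules, so loss here alone is unlikely; the source file settles it.

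Several limits on the illustration stand:

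- Section 6.6 assigns 0.025 only to the two primary IGA hypotheses. The level reaching itch depends on Figure JAHL.6.1, which is not reproduced in the text reviewed. At 20% vs 10% censoring, the 55% becomes 67% at alpha 0.05 and 31% at 0.005.
- The censoring gaps are assumed. A 5-point gap gives only 10% to 12%, and equal censoring gives no inflation.
- Rescue topical steroid is first scheduled for dispensing at Week 1, so rescue censoring should be low at Weeks 1 and 2. Unless many diary entries are missing, rates near 99% there would be conspicuous.
- In the tipping-point analysis missing responses are drawn directly from response probabilities, so the rule touches observed patients only. The Cox analysis does not use this cell.

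These points limit how far the error would distort results. They do not make the rule correct.

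**Conclusion.** The rule is wrong as written and must be corrected. It contradicts its own label and sign convention, and it would misclassify most patients if followed: 74 of 77 score pairs respond instead of 28. It defines 12 of the 36 multiplicity-controlled hypotheses and one of the three subgroup endpoints. That conclusion rests only on the SAP's own definitions and needs no assumption about data.

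The size of the inferential harm does rest on assumptions: the itch distribution, the censoring rates, the alpha reaching itch, and an unadjusted test. With those, false rejection ranges from nominal at equal censoring to 95% at 40% vs 20%. A dropped minus sign is the most likely cause, and nothing in the documents shows that the rule was programmed this way.

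**What to change.** In Table JAHL.6.6, change the itch responder derivation to a change from baseline of ≤ -4 with baseline ≥ 4, after confirming against the source file that the minus sign is absent. Check every program specification drawn from that cell, including those for the pMI, tipping-point, per-protocol and subgroup analyses.

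Optionally, state that patients with baseline Itch NRS below 4 or missing are outside the denominator and are not imputed as nonresponders. Table JAHL.6.7 already implies this.

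The cost is one character in the SAP and a specification check. Design, data collection and sample size do not change.

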4.3. Exploratory Objectives

The exploratory objectives of this study are the following:

Objectives/Endpoints

• Mean change from baseline in nocturnal itch assessed by actigraphy device at 1 week and 4 weeks• Frequency of patient-reported “no itch” (Itch NRS score = 0) days from daily diaries from Week 12 to Week 16• Frequency of patient-reported “no pain” (Skin Pain NRS score = 0) days from daily diaries from Week 12 to Week 16• Mean change from baseline in the score of Item 1 of the ADSS at 1 week and 16 weeks• Mean change from baseline in the score of Item 3 of the ADSS at 1 week and 16 weeks• To evaluate changes from baseline in immunoglobulin E levels during the study• To evaluate changes from baseline in eosinophil levels during the study• To characterize baricitinib pharmacokinetics in the AD population and explore relationships between baricitinib exposure and study endpoints• To assess time to 4-pt itch reduction during the first 14 days after initiation of treatment• To assess time to improvement in Skin Pain during the first 14 days after the initiation of treatment• To assess the use of rescue therapy through the weight of sponsor provided topical corticosteroid and number of days not using rescue therapy

5. Study Design

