		Itch-free days (Itch NRS = 0)	Count of observed value = 0 for 28-day (4-week) intervals starting on the day of the first study drug administration. This will be calculated for the following visit intervals: baseline to Week 4, Week 4 to Week 8, Week 8 to Week 12 and Week 12 to Week 16. Day 1 is defined as the day of first study drug administration therefore the baseline to Week 4 assessment is based on Day 1 to Day 28, Week 4 to Week 8 is based on Day 29 to Day 56, etc.	If patients do not have at least 16 non-missing assessments in each 4-week interval, the score is missing.
Skin Pain Numeric Rating Scale (NRS)	Skin Pain NRS is a patient-administered, 11-point horizontal scale anchored at 0 and 10, with 0 representing “no pain” and 10 representing “worst pain imaginable.” Overall severity of a patient’s skin pain is indicated by selecting the number that best describes the worst level of skin pain in the	Skin Pain NRS score	Single item; range 0 to 10. Refer to Section 6.2.2 on how to derive the visit score.	Refer to Section 6.2.2 on how to derive the visit score.
		Change from baseline in Skin Pain NRS	Change from baseline: observed skin pain score – baseline skin pain score	Missing if baseline or observed value is missing.

Measure	Description	Variable	Derivation / Comment	Imputation Approach if Missing Components
	past 24 hours Refer to Section 6.2.2 for details on how to calculate the weekly score which will be used in the continuous analysis.	Pain-free days (Skin pain NRS = 0)	Count of observed value = 0 for 28-day (4-week) intervals starting on the day of the first study drug administration. This will be calculated for the following visit intervals: baseline to Week 4, Week 4 to Week 8, Week 8 to Week 12 and Week 12 to Week 16. Thus, if Day 1 is defined as the day of first study drug administration, the baseline to Week 4 assessment is based on Day 1 to Day 28, Week 4 to Week 8 is based on Day 29 to Day 56, etc.	If patients do not have at least 16 non-missing assessments in each 4-week interval, the score is missing.

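### Itch-free and pain-free days are unscaled counts over 28 days with as few as 16 observed, so the arm summaries mix symptom control with diary completion

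*SAP*

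**What the plan says.** Table JAHL.6.6 in SAP Section 6.12 gives the itch row and the skin pain row the same derivation: "Count of observed value = 0 for 28-day (4-week) intervals starting on the day of the first study drug administration". The intervals are fixed study days from first dose: Days 1 to 28, Days 29 to 56 and, by extension, Days 57 to 84 and 85 to 112. The entry for missing components is "If patients do not have at least 16 non-missing assessments in each 4-week interval, the score is missing".

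Table JAHL.6.7 lists the analysed variables as "Number of Itch-free (Itch NRS = 0) Days" and "Number of Skin Pain-free (Skin pain NRS = 0) Days". Each is an exploratory analysis by descriptive statistics in the ITT population, with the entry "No comparisons; Week 12 to 16". SAP Section 4.3 and protocol Section 4 also place them among the exploratory objectives, as the frequency of no-itch and no-pain "days from daily diaries from Week 12 to Week 16".

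Neither document gives a denominator, a scaling rule or an imputation for single diary days inside this count. Table JAHL.6.1 and Section 6.4 work at the level of the endpoint or visit. On the primary censoring rule, which removes data after rescue or permanent drug discontinuation, Section 6.4 says: "This censoring rule will be applied to all continuous and categorical efficacy and health outcome endpoints". It does not say how the rule operates within a 28-day count.

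**The concern.** A count of zeros over a varying number of recorded days measures two things at once: how often the patient was free of symptoms, and how often the diary was filled in. The SAP does not call a missing day symptomatic, but such a day contributes 0 to the total, just as a day with a score of 1 or more does.

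The plan's other diary measures do not behave this way. The weekly diary scores in Section 6.2.2 are means of the recorded days with at least 4 of 7 present. That is the same 57% threshold (4/7 = 16/28), but in a mean a missing day does not by itself move the score. Section 6.9.1 reports time without rescue therapy as a proportion.

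What is at stake is the description of each arm. Every arm's mean is pulled down by incomplete diaries. If completion differs between arms, the means differ with no difference in itch or pain, and readers will set those means side by side even though no test is planned.

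**Working it through.** The documents state no figure for this endpoint, so there is nothing to reproduce. The inputs are the 28-day interval and the 16-day minimum (Table JAHL.6.6), and the Week 16 visit timing and diary arrangements (protocol Section 2). The symptom-free rate p and the completion rates are assumptions, because the documents give neither.

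**1. The floor.** 16/28 = 57.1% of days must be recorded, so up to 12/28 = 42.9% may be missing.

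**2. Shortfall for one patient.** With m recorded days, and missed entries unrelated to symptoms, the expected count is p × m. The full-interval value is p × 28. The shortfall is p × (28 − m), a relative loss of (28 − m)/28 whatever p is.

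| Recorded days m | p = 0.25 | p = 0.50 | p = 0.75 | p = 1 | Relative loss |
|---|---|---|---|---|---|
| 16 | 4 vs 7 | 8 vs 14 | 12 vs 21 | 16 vs 28 | 43% |
| 20 | 5 vs 7 | 10 vs 14 | 15 vs 21 | 20 vs 28 | 29% |
| 24 | 6 vs 7 | 12 vs 14 | 18 vs 21 | 24 vs 28 | 14% |
| 28 | 7 vs 7 | 14 vs 14 | 21 vs 21 | 28 vs 28 | 0% |

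(Each cell is the SAP count against the full 28-day value.)

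**3. Same count, different frequency.** Sixteen zeros in 16 recorded days is 100% symptom-free. Sixteen zeros in 28 is 16/28 = 57.1%. The SAP count is 16 for both.

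**4. Two arms with the same p.** If completion differs by 10 percentage points (say 75% against 85%, assumed), the means differ by 28 × 0.10 × p:
- p = 0.10: 0.28, about 0.3 days
- p = 0.25: 0.7 days
- p = 0.50: 1.4 days
- p = 1: 2.8 days

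**5. Full adherence does not always remove it.** The Schedule of Activities puts the Week 16 visit 112 days after randomization, ±4 days. Taking first dose on the randomization day as Day 1, the earliest visit is Study Day 109. Footnote g keeps the diary going after that visit only for patients not entering the extension study. A fully adherent patient who enters the extension then has Days 85 to 109 (25 days), or 24 if the last entry is the day before the visit. If always symptom-free, this patient loses 3/28 = 11% to 4/28 = 14%. The Week 16 weekly window in Section 6.2.2 is anchored on the visit; this count is not.

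**6. Why plain rescaling is not enough.** Take a patient with 8 zeros in the first 16 days of the interval who is rescued on the next day, and suppose the primary censoring rule applies. The SAP count is 8. Plain rescaling gives 28 × 8/16 = 14, which carries the pre-rescue rate onto the 12 censored days. Keeping those 12 days in the denominator as not symptom-free gives 8/28 = 28.6%, or 8 days of 28.

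**The case against.** The strongest reply is that little depends on these variables. They are exploratory, descriptive and outside the multiplicity scheme, with no comparison planned. Itch and skin pain are also analysed through weekly means, which feed the secondary and key secondary analyses and lack this feature. That stands, and it fixes the weight of the point. A reader might infer that the trial's treatment comparisons on itch or pain are biased; the documents do not support that.

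Second, the variable is what its label says, a number of observed days, and giving no credit for unobserved days resembles the plan's conservative rules elsewhere: nonresponder imputation in Section 6.4.1, and missing daily itch treated as non-response in the time-to-event analysis of Section 6.2.3. This stands only in part. Those rules are stated as imputations, whereas here the effect is an unstated by-product of counting. The objective also speaks of a frequency, which a proportion serves at least as well.

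Third, 43% applies only to a patient exactly at the 16-day floor, and 2.8 days needs an assumed completion gap together with patients symptom-free every day. That stands, hence the range over p. A reader might also infer that completion did differ by arm; nothing in the documents shows it.

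Fourth, simple rescaling would contradict the assumption in Section 6.11.2 that response disappears after rescue or permanent discontinuation. That stands and shapes the fix.

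**Conclusion.** The concern holds as a minor one. The derivation as written understates symptom-free days for any patient who has some such days and 16 to 27 days recorded. The loss is at most 43% and shrinks as completion rises; below 16 days the score is missing altogether. A 10-point completion gap between arms would produce a difference of 0.3 to 2.8 days for p from 0.10 to 1. These sizes rest on missed entries being unrelated to symptoms and on assumed completion rates. No primary or key secondary result is affected, and no test depends on the count.

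**What to change.** In both rows of Table JAHL.6.6, define the score as the percentage of diary days with score 0, or 28 times that proportion, and keep the 16-day minimum. Define the denominator in one sentence:
- Leave out skipped diary days and days after an early Week 16 visit.
- Keep days censored for rescue or permanent drug discontinuation in it, as not symptom-free, in line with Section 6.11.2.

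The same sentence should say whether censored days count towards the 16. Tabulate the number of observed days by arm beside the summary.

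This is a cheap improvement: a short change of derivation and one extra table line, with no new data and no change to the testing scheme. Its downside is the assumption that skipped days resemble recorded days, which the table of observed days lets a reader weigh.
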